Role of MPOD in circadian photoreception: Nagare et al. have recently conducted a series of within-subjects nighttime studies recording light-induced melatonin suppression in human subjects exposed for 1 h to white light sources with CCTs ranging from 3300 K to 5000 K. Measurements for MPOD were performed using a non-invasive instrument employing psychophysical optical technique based on heterochromatic flicker photometry to determine MPOD's role in circadian photoreception. It was observed that a higher MPOD was significantly correlated with lower melatonin suppression, wherein the macular pigment acted as a filter, lowering the absolute circadian sensitivity (Fig. 2). **The effect size of this observation further indicated that about 35% of the light incident on cornea was being modulated by the macular pigment for the rectangular light sources used in the study.**

These studies were performed using healthy young adults and our proposal will extend these results to include older adults, including those with MCI, who have been shown to be less sensitive to light overall. Moreover, preliminary data from our lab using a protocol similar to the one described here (results described in introduction) showed that light delivered on axis is almost twice as effective as light delivered off axis. Therefore, in order to deliver a robust light-dark pattern to promote entrainment and minimize nighttime melatonin suppression, a better understanding of the retinal mechanisms associated with circadian phototransduction is needed.

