Participant selection: Following IRB approval, we will recruit 24 MCI participants and 24 healthy, age-matched controls through e-mail notices, posters, and word-of-mouth. MPOD will be assessed at the recruitment stage for all subjects to determine their initial eligibility, which will require subjects to fit into one of 2 distinct groups (low: MPOD < 0.3, high: MPOD > 0.5). **Eligible participants will be MCI or mild AD patients who are 55 years and older.** We will work with our physician collaborators in the area (who are currently working with the PIs in 3 other R01s) to perform the pre-selection diagnosis according to the following **pre-selection criteria:** Participants must be diagnosed by their physician with amnestic MCI or mild AD. Subjects in the control group will have normal cognition. Study participants who meet the following inclusion and exclusion will discuss informed consent for study participation: **Inclusion criteria:** Those taking antidepressants will be included, but type of medicine and dosage intake will be monitored. There will be no exclusions based gender, race, and ethnicity. Participants must also not meet the following **Exclusion criteria:** Presence of another brain disease that fully explains the dementia (extensive brain vascular disease, Parkinson's disease, dementia with Lewy bodies, traumatic brain injury, or multiple sclerosis); residence in a skilled nursing facility or long-term care; indication for psychiatric hospitalization or acute suicidality in the opinion of the physician; major organ failure (e.g., kidney failure); or uncontrolled generalized disorders such as hypertension or diabetes. Exclusion criteria will also extend to obstructing cataracts, macular degeneration, and blindness. Those taking over-the-counter melatonin, prescription sleep medication or beta blockers will be excluded. We will review the participants' ophthalmologic tests during selection and exclude those who have undergone

[figure not shown]

Fig. 2. Correlation between MPOD and melatonin suppression showing pooled data from a series of within-subjects nighttime studies. Each yellow diamond corresponds to suppression data for an individual subject. The black line corresponds to the best fit linear regression model. All subjects underwent a 1-h exposure to white light sources with CCTs ranging

[figure not shown]

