Sample Size and Estimated Power. The study will have enough power to detect treatment differences. Previous work by our lab⁷⁴ provides measures of variability for our primary outcome measures (melatonin suppression and questionnaires). In particular, a prior within subjects' study⁷⁴ involving effects of white light on nighttime melatonin suppression have shown that a sample size of 12 or more participants is enough to detect statistically significant ($\alpha = 0.05$) difference in suppression ($\approx 14\%$) for a large effect (Cohen's $d > 0.5$) at a statistical power $\approx 95\%$. A sample size of 19 subjects (24 subjects, 20% attrition) for each group, therefore, should be sufficient for the detection of significant differences in melatonin suppression.

Data and Statistical Analyses

Anticipated Outcomes. Our hypothesis is that greater melatonin suppression will be observed for the on-axis interventions, compared to the off-axis interventions, due to 2 reasons: (1) the greater density of cone photoreceptors in central retina (which will account for about 12% melatonin suppression difference according to CS model calculations⁷⁰) and (2) the *Stiles-Crawford* effect, which suggests that the most effective optical rays incident on the retina are along the foveal axis. Overall, we also expect to see greater melatonin suppression for the low MPOD group compared to the high MPOD group, as higher MPOD means greater attenuation of the photic stimulus. We further hypothesize a significant interaction between the effect of MPOD and light source spectrum, as the yellow macular pigment preferentially filters out short-wavelength radiation, and hence should only attenuate the blue light stimulus. In other words, for high MPOD subjects, we expect to see greater melatonin suppression following exposure to the green light as compared to the blue light exposure. Lastly, we expect to observe a significant interaction between the effect of MPOD and lighting distribution, as since the yellow macular pigment is located primarily in the central retina, the off-axis dose should not be affected by it. Finally, we hypothesize that lower MPOD scores will be associated with lower cognition.

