Overall Analyses will include (1) evaluation to determine data quality, (2) creation of constructed variables and determination of variable distributions, (3) applying tests of parametric statistical assumptions wherever appropriate, (4) preliminary (generally bivariate) testing of hypotheses, (5) consideration of potential covariates to build into the statistical models to increase the probability of detecting treatment effects if they exist, and (6) development and elaboration of multivariate models. SPSS software (V25, IBM, Armonk, NY, USA) will be used for all statistical analyses (significance, $p < 0.05$). [name] will perform all statistical analyses and work with Drs. [name] and [name] on statistical analyses.

Aims 1, 2: In order to evaluate outcomes of the intervention, we will first determine the melatonin suppression for each condition by comparing melatonin levels collected during the dim-light control week to those at the same time in the experimental conditions' weeks. We will then perform a mixed-model analysis of variance (ANOVA), with lighting distribution (on-axis vs. off-axis) and spectrum (blue light vs. green light) serving as the within-subjects factors, and MPOD group (high MPOD > 0.5 vs. low MPOD < 0.3) and cognitive status (MoCA scores) (healthy vs. MCI participants) serving as the between-subjects factors. Mixed model analyses allow for different numbers of observations for different subjects (e.g. if there are dropouts). As sample size and its associated degrees of freedom allow, we will also adjust for covariates that may be associated with outcome measures, such as retinal illuminance, gender, season and any medication load. Within the limits of the sample, we will explore treatment-covariate interactions for each participant-level covariate. If strong interactions are observed, it will suggest that a future study could possibly be stratified on the given factor. To further assess the impact of MPOD on individual light sensitivity, a Pearson correlation coefficient will be calculated between melatonin suppression and MPOD values recorded across MCI patients and healthy older adults. We hypothesize a negative correlation, wherein higher MPOD values will be associated with lower suppression.

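### The stated power of about 95% with 12 participants cannot be reproduced at the printed effect-size threshold, and this within-subject figure does not support 19 per group for the between-subject comparisons of melatonin suppression

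*Combined protocol and SAP*

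**What the plan says.** The section Sample Size and Estimated Power opens with the assurance that "The study will have enough power to detect treatment differences". The support is one prior within-subject study of white light, from which the plan takes that "a sample size of 12 or more participants is enough to detect statistically significant" differences (alpha 0.05, about 14% suppression) "for a large effect (Cohen's $d > 0.5$) at a statistical power" of about 95%. It then reasons that 19 subjects in each group, after 20% attrition from 24, "should be sufficient for the detection of significant differences in melatonin suppression". No SD, within-person correlation, test or sidedness is printed.

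Under Data and Statistical Analyses (Aims 1, 2), the mixed-model ANOVA of melatonin suppression is specified "with lighting distribution (on-axis vs. off-axis) and spectrum (blue light vs. green light) serving as the within-subjects factors", with MPOD group "and cognitive status (MoCA scores) (healthy vs. MCI participants) serving as the between-subjects factors". The Anticipated Outcomes paragraph hypothesises more suppression in the low MPOD group, and interactions of MPOD with spectrum and with distribution. Participant selection fixes 24 MCI participants and 24 controls. For MPOD it says only that eligibility depends on a recruitment measurement "which will require subjects to fit into one of 2 distinct groups (low: MPOD < 0.3, high: MPOD > 0.5"), with no target number in either stratum.

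**The concern.** Two things look wrong.

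- **The figure.** If power of about 95% with 12 participants is claimed for effects above 0.5, a reader will check it at 0.5. There it falls far short. This is the only quantitative support for the sample size.
- **The inference.** A within-subject result is carried to a per-group sample size and to differences in suppression generally. The analysis also compares different people on that outcome (low versus high MPOD, MCI versus healthy). Those main effects depend on between-person variance and gain nothing from pairing.

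At stake is how a null result would be read. If the plan calls the sample sufficient without qualification, a non-significant MPOD-group or cognitive-status effect may be taken as evidence of no difference, although the plan gives no basis for knowing what difference could have been detected.

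**Working it through.** **Inputs.** From Sample Size and Estimated Power: n = 12, alpha 0.05, d > 0.5, difference about 14%, power about 95%, 24 enrolled and 19 evaluable per group. From Anticipated Outcomes: about 12% difference in suppression attributed to cone density. My assumptions: two-sided tests unless noted, and both percentages read as points of suppression.

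**Attrition.** 24 × 0.8 = 19.2, so 19 per group reproduces, and 38 pooled.

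**The plan's 95%.** For a paired t-test, power comes from the noncentral t with n − 1 degrees of freedom and noncentrality dz × √n, where dz is the mean difference divided by the SD of within-person differences.

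| n | Power at dz = 0.5, two-sided | One-sided |
|---|---|---|
| 12 | 35% | 49% |
| 19 | 54% | 67% |
| 38 | 85% | 92% |

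At n = 12 and dz = 0.8, power is 71% two-sided (83% one-sided). A repeated-measures ANOVA with f = d/2 = 0.25, over 2 to 8 measurements and correlations of 0.3 to 0.7 (assumed), gives 27% to 90%. None of these reaches 95%.

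**What would give 95% at n = 12.**
- dz = 1.146 two-sided (1.015 one-sided). For 14 points, this means an SD of differences of 14 / 1.146 = 12.2 points. By contrast, dz = 0.5 means 14 / 0.5 = 28 points.
- If d is scaled on the raw SD, dz = d / √(2(1 − r)). Setting d = 0.5 and dz = 1.146 gives r = 1 − (0.5 / 1.146)² / 2 = 0.905.

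**Largest SD of within-person differences for 80% power** (two-sided paired test, one spectrum). The required dz is 0.680 at n = 19 and 0.467 at n = 38.

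| Difference | n = 19 | n = 38 |
|---|---|---|
| 14 points | 14 / 0.680 = 20.6 | 14 / 0.467 = 30.0 |
| 12 points | 12 / 0.680 = 17.6 | 12 / 0.467 = 25.7 |

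**Between-subject comparisons.** For two groups of 19, power comes from the noncentral t with 36 degrees of freedom and noncentrality d / √(1/19 + 1/19). For a single lighting condition, 80% power needs d = 0.93 between-subject SD. If 0.5 is used as an illustration only, power is 32%; an assumed MPOD split of 10 versus 28 gives 26%.

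The opposite illustration takes the 95% claim at face value (SD of differences 12.2) and assumes a 14-point group difference. The between-subject SD is then 12.2 / √(2(1 − r)).

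| Assumed r | Between-subject SD (points) | Power, 19 vs 19, one condition |
|---|---|---|
| 0.3 | 10.3 | 98% |
| 0.5 | 12.2 | 93% |
| 0.7 | 15.8 | 76% |
| 0.9 | 27.3 | 34% |

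The printed inputs cannot tell these cases apart. The last row matters most: a correlation of about 0.90, which would rescue the within-subject figure at a raw-scale d of 0.5, is also the one under which between-subject power is poor.

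**The case against.** The strongest reply is that the plan prints an inequality. A standardised difference of 1.15 satisfies d > 0.5, so the 95% is not contradicted, and the values behind it belong to a cited study that is not reproduced here. Reading 0.5 as Cohen's f also gives 95.2% at n = 12 (three measurements, correlation 0.5, both assumed). This stands as a limit: the prior result is not shown to be wrong. It does not rescue the text. The plan prints d, and a power claim attached to a threshold should hold at the threshold.

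A reader might infer that the main contrast of Aim 1 is underpowered. The documents do not support that. Preliminary Data reports that "light delivered on axis is almost twice as effective as light delivered off axis", and 38 pooled completers give 85% even at dz = 0.5 in one spectrum.

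A reader might also infer that the MPOD-group and cognitive-status tests have low power. That is not shown either. The 32% borrows an effect size printed for a different contrast, and the face-value calculation runs from 34% to 98%.

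Finally, the opening sentence speaks of treatment differences, which are the within-subject lighting contrasts, and the documents describe the study as exploratory and a feasibility study. That narrows the claim's likely intent. But the conclusion on 19 per group is worded for differences in suppression without limit, and the same section goes on to hypothesise an MPOD-group difference on that outcome.

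**Conclusion.** The concern holds in a limited form and should be fixed. At the printed threshold, power with 12 participants is 35% two-sided (49% one-sided), not about 95%. The stated power needs dz of about 1.15, or a raw-scale d of 0.5 with a correlation of about 0.90, and the plan prints neither. The figure is therefore unverifiable as written rather than proven false. Separately, a within-subject figure gives no support for calling 19 per group sufficient for the MPOD-group and cognitive-status comparisons. Their power is unknown, because the between-subject SD and the MPOD split are not given.

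The paired and two-sample figures assume a t-test at alpha 0.05. The pooled figure assumes 19 completers in each group and a common on-axis versus off-axis effect across groups.

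**What to change.** Rewrite the sample-size paragraph in two respects.

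1. **Within-subject contrast.** Replace d > 0.5 and about 95% with the dz or SD of within-person differences actually used, the test and the sidedness. Restate on-axis versus off-axis power at n = 19 and n = 38, and say whether it is for one spectrum or averaged over both. If only d = 0.5 can be supported, state the lower power. If no SD can be given, state the largest SD of within-person differences that gives 80% power (two-sided paired test, one spectrum): about 21 points (n = 19) or 30 points (n = 38) for a 14-point difference, and about 18 or 26 for the 12 points attributed to cone density.
2. **Between-subject comparisons.** Limit the power claim to the within-subject lighting contrasts. Add the difference detectable with 80% power for cognitive status at 19 versus 19 (0.93 between-subject SD for one condition, converted to suppression points with the prior SD). Add the same for MPOD group at the low/high split the study expects. Note that the MPOD effect is expected mainly under blue on-axis light, so averaging over the four conditions would dilute it. If a detectable correlation is given for Aim 2, note that excluding MPOD from 0.3 to 0.5 means it is not a population correlation.

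The cost is one reworded paragraph, with no change to sample, design or analysis. The downside is that the stated figures become less favourable.

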Melatonin Suppression Protocol: On each study night, participants will be required to arrive at the laboratory at 23:30 and remain in dim light (< 5 lux at the eye) for 30 min, followed by a 60-min exposure to one of the 4 experimental conditions (Fig. 5). To ensure consistency of the light distribution with regard to the participants' line of sight over the course of the 1-h exposure, all participants will perform a simple on-axis visual task that involves responding (using a hand-held tally counter) to a flashing, pre-programmed RGB LED source (generic low-power) suspended in the center of the desktop luminaire (see Fig. 4). The visual task will not be performed on the dim-light control night, when participants will be free to operate their personal electronic devices (i.e., iPads, tablets, cell phones, etc.). However, all displays will be covered with orange-tinted media (Roscolux #21 golden amber, Rosco Laboratories, Stamford, CT, USA) to filter out radiation < 525 nm to prevent participants from receiving circadian-effective light from their self-luminous devices. In a previous study, photometric measurements of the stimulus emitted by similarly filtered electronic displays revealed light lev-

Time (hh:mm)	23:30	24:00	00:30	01:00
Condition	Dim light	On axis (CS = 0.40, 27 lux)		
		Off axis (CS = 0.40, 27 lux)		
Saliva sample		Dim-light (CS < 0.10, < 5 lux)		
			S1	S2
				S3

Fig. 5. Experimental protocol showing the relationship between on-axis and off-axis conditions, and salivary melatonin sample times (S1 [0 min], S2 [30 min], and S3 [60 min]).

els of < 5 lux, which translated to a CS of < 0.001⁷³.

Over the course of each experimental session, 3 saliva samples (S1, S2, S3) will be collected from each participant for melatonin analysis. Saliva samples (1 ml) will be collected using the Salivette system (Sarstedt, Nümbrecht, DE), wherein the participant chews on a plain cotton cylinder for 1-2 min, which is immediately placed in a test tube, centrifuged for 5 min at 1000 g, and frozen (-20 °C). The frozen samples from each session will be assayed in a single batch using melatonin radioimmunoassay kits (Direct Melatonin RIA, ALPCO, Salem, NH, USA).

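### The 0-min saliva sample S1 has no stated role in the suppression analysis; using it as a pre-specified covariate, and naming the analysed time point, would be a cheap gain

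*Combined protocol and SAP*

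**What the plan says.** Under Melatonin Suppression Protocol, "3 saliva samples (S1, S2, S3) will be collected from each participant for melatonin analysis" in each session. The Fig. 5 caption places them at 0, 30 and 60 min of exposure. Participants arrive at 23:30 and spend 30 min in dim light, so S1 falls at 24:00, before any experimental light. On assay, "The frozen samples from each session will be assayed in a single batch".

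Under Data and Statistical Analyses, Aims 1, 2, suppression comes from "comparing melatonin levels collected during the dim-light control week to those at the same time" in the experimental weeks. No formula or time point is given. The model is a mixed-model ANOVA with "lighting distribution (on-axis vs. off-axis) and spectrum (blue light vs. green light) serving as the within-subjects factors", and MPOD group and cognitive status between subjects. Covariates are introduced with "such as retinal illuminance, gender, season and any medication load", as sample size allows. Step (5) of the overall analyses plans "consideration of potential covariates to build into the statistical models to increase the probability of detecting treatment effects if they exist".

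Two other places matter. Participant selection excludes anyone with low melatonin at 24:00 on the dim-light night, which is run first; by the timing above, that is apparently S1. Potential pitfalls judges experimental validity by a main effect of exposure duration, 60 min against 30 min.

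**The concern.** Each person contributes one dim night and four light nights. Someone whose melatonin runs high or early on one night has raised values in all of that night's samples. Comparing light and dim nights at the same clock time does not remove this. The shared dim night cancels from on-axis minus off-axis on a log-ratio scale, but the light nights' own shifts do not. S1 is the only pre-light sample on those nights, so it is the only one that could absorb them. If the assay sentence means one batch per session, S1 would also carry any batch shift of that night.

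At stake is precision in the on-off and blue-green contrasts and in their interactions with MPOD group; Anticipated Outcomes expects both MPOD interactions to be significant. Two further gaps sit alongside. The ANOVA and the Aim 2 Pearson correlation could each use 30-min, 60-min or averaged suppression. And the stated ANOVA has no term that yields the duration effect used as the validity check.

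**Working it through.** **Text check.** S1 appears in sample collection and, apparently, in the 24:00 exclusion. It is absent from the suppression definition, the ANOVA factors and the named covariates. Duration appears only under Potential pitfalls.

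**Inputs from the documents.** Four light nights per person. "A sample size of 19 subjects (24 subjects, 20% attrition) for each group": 24 × 0.8 = 19.2, so 19 per group and 38 in all. Two-sided 5% is used (the plan gives p < 0.05 without sidedness). There is no stated figure to reproduce on this point.

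**Assumed inputs, log scale.** Night SD sn 0.15, 0.25 or 0.35; residual SD se 0.10 or 0.15; correlation rho of the night shift between S1 and the later sample 0.6 or 0.8; person-to-person SD of the on-off response tau 0, 0.15 or 0.30. S1 and the later sample are given equal variance.

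**Formulas.** The on-off contrast averaged over blue and green weights four nights by ±1/2, so night and residual variation contribute 4 × (1/4) × (sn² + se²).
- Unadjusted SD = √(sn² + se² + tau²).
- Correlation of S1 with the later sample: rel = rho·sn²/(sn² + se²).
- Adjusted SD = √((sn² + se²)(1 − rel²) + tau²).

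**Example with a large gain** (sn 0.35, se 0.10, rho 0.8, tau 0.15). rel = 0.098/0.1325 = 0.740. Unadjusted √0.155 = 0.394; adjusted √(0.1325 × 0.453 + 0.0225) = 0.287. Cut 27%.

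**Example with a small gain** (sn 0.15, se 0.15, rho 0.6, tau 0.15). rel = 0.0135/0.045 = 0.30. Unadjusted 0.260; adjusted 0.252. Cut 3%.

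**Power.** Assume 40% suppression on-axis against 28% off-axis. The effect is ln(0.72/0.60) = 0.182. Power is noncentral t with n − 1 degrees of freedom, over the whole grid:

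| tau | Cut in SD | Power, all 38: without S1 → with S1 | Power, one group of 19: without S1 → with S1 |
|---|---|---|---|
| 0 | 5-33% | not tabulated | not tabulated |
| 0.15 | 3-27% | 76 to >99% → 86 to >99% | 45-89% → 55-94% |
| 0.30 | 2-18% | 62-88% → 69-90% | 34-57% → 39-61% |

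Gains are smallest where power is already high: at sn 0.15, se 0.10, rho 0.8, tau 0.15, one group of 19 moves from 89% to 94%.

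The MPOD-by-distribution interaction compares the same contrast between MPOD groups, so the same percentage cuts apply. No power is computed for it.

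**Sensitivity.**
- Residual error larger than night variation (sn 0.10, se 0.20): cut of 2% or less, even at rho 1.
- One assay batch per session with an assumed batch SD sb of 0.10: rel = (rho·sn² + sb²)/(sn² + se² + sb²). At sn = se = 0.15 and tau 0, the cut rises from 5-8% to 10-14%.
- S1 double ratio (later log ratio minus S1 log ratio) at sn = se = 0.15, tau 0: the SD grows by 0%, 10% and 18% at rho 1, 0.8 and 0.6.

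**Duration check.** One dim night serves four ratios. The 60-minus-30-min log difference has variance 2se² per night, so a person's mean over four ratios has variance 2se²/4 + 2se² = 2.5se². Treating the sessions as independent gives 4se²/4 = se². A nominal 5% test then rejects with probability 2[1 − Φ(1.96/√2.5)] = 21.5%. One value per person avoids this.

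**The case against.** The strongest reply is that this is an efficiency preference resting on unknown SDs. The covariate list is open, step (5) invites precision covariates, the study calls itself exploratory, and the gain may be 2% or less. All of that is correct and limits the point to an inexpensive improvement.

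The effect size may also be too small. Anticipated Outcomes ties the 12 points to cone density alone and adds the Stiles-Crawford effect; Preliminary Data describes on-axis light as almost twice as effective. With an assumed 40% against 20%, 19 people have 85% power without S1 at sn 0.35, se 0.10, tau 0.15, and 98% with it (rho 0.8). A larger true gap leaves less power to gain. The ANOVA also pools both cognitive groups, so the 38-person column is the relevant one for the distribution main effect.

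A reader might infer more than the documents support:
- That the on-off contrast is biased. The four light conditions are counterbalanced, and the issue is noise only.
- That S1 is unused or ruled out. The 24:00 exclusion apparently uses it, and nothing bars it as a covariate.
- That the duration check contradicts the ANOVA. S2 and S3 allow a separate test; it is simply not written down.
- That noise could trigger the planned re-run. That step is tied to chromatic adaptation, a different cause.
- That the open time point inflates type I error. Free choice among 30 min, 60 min and their mean after seeing the data would give about 7-11% (n = 19, correlations 0.9 to 0.3), but nothing says the choice will be made that way.

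**Conclusion.** The point holds as a gap in specification with a low-cost remedy. S1 has no stated role in the suppression analysis, the analysed time point is not named, and the stated ANOVA cannot supply the duration effect. The likely benefit runs from negligible to about a one-third cut in the SD of the on-off contrast, depending on how far night-to-night shifts exceed residual error and how closely S1 tracks them. Every SD and correlation is assumed, so these figures show a range and do not predict the gain. The improvement is optional to recommended; the planned analysis is not invalid without it.

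**What to change.** State in the SAP:
1. One suppression value per person per night, for example log(light/dim), at one named time point or as the mean of 30 and 60 min. Use it for the ANOVA and the Pearson correlation alike.
2. log(S1 light night / S1 dim night) as a pre-specified night-level covariate, with one slope pooled over the four light nights, in a linear mixed model with random person, person-by-distribution and person-by-spectrum terms. A standard repeated-measures ANOVA does not take a covariate that varies by night. A person effect alone is not enough: in null simulations with 38 people and tau 0.30, it gave 9-21% type I error for the on-off test, against about 5% with person-by-distribution variation as the error. Do not make the S1 double ratio the primary outcome.
3. The duration check as a separate analysis, one value per person: the mean over the four light nights of the 60-min minus the 30-min log ratio, tested against zero.

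Cost: a few lines of text and code and one degree of freedom; no new samples. If sample error dominates there is little or no gain: at sn 0.10, se 0.20 and rho 0.6-0.8, the standard error changes by −1.1% to +0.5%. Fitting the S1 slope from the on-off contrasts alone, instead of pooling, would cost up to 2.5 points of power in a group of 19.
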